#### **4.4. Visit Schedule**

A Screening Visit will be conducted up to 2 weeks prior to enrollment, and subjects will be treated with investigational product at the Day 1 Visit for GL and at the Week 2 visit for FHL. Following each treatment, subjects will complete a paper diary for 2 weeks to capture their assessment of improvement or satisfaction with the appearance of GL and FHL. Follow-up safety phone calls will be conducted at Weeks 1 and 3. Post-treatment on-site follow-up visits will occur at Weeks 2, 4, 6, 10, 14, 18, 22, 26, 30, 34, and 38. The total study duration will be up to 40 weeks, including up to 2 weeks for screening. Subjects will be followed for a minimum of 24 weeks from GL treatment for safety or until all scores on the IGA-FWS and PFWS, as well as the IGA-FHWS and PFHWS, return to baseline (Day 1 Visit prior to GL treatment) or until Week 38, whichever occurs first. Subjects will then have a Final Evaluation Visit. If the DRC elects not to proceed with the FHL injection in a given dose cohort, subjects assigned to that cohort who have already received GL treatment will be followed for 14 weeks from the time of treatment (Day 1).

Subjects will be evaluated for FHL severity using the Revance-validated 4-point IGA-FHWS and PFHWS at rest and at maximum eyebrow elevation. In addition, to determine the efficacy

response to GL subjects will be evaluated for improvement to a score of 0 or 1 (none or mild) on the IGA-FWS and the PFWS at rest and at maximum frown.

## 5. Study Population

Approximately 60 female or male subjects, 18 to 65 years of age, with moderate to severe GL and FHL will be enrolled. Investigators will make all reasonable efforts to enroll equal proportions of patients with moderate and severe FHL (based on baseline assessments) in each dosing cohort. Subjects must meet all of the inclusion criteria and none of the exclusion criteria to be eligible for the study.

### 5.1. Inclusion Criteria

To be eligible for participation, subjects must:

1. Provide written informed consent consistent with ICH-GCP guidelines and local laws, including authorization to release health information, signed prior to any study procedures being performed
2. Be outpatient, male or female subjects, in good general health, 18 to 65 years of age
3. Have a score of moderate (2) or severe (3) FHL during maximum contraction (eyebrow elevation) as assessed by the IGA-FHWS
4. Have a score of moderate (2) or severe (3) FHL during maximum contraction (eyebrow elevation) as assessed by the PFHWS
5. Have a score of moderate (2) or severe (3) GL during maximum frown based on the IGA-FWS scale
6. Have a score of moderate (2) or severe (3) on GL during maximum frown as assessed by the PFWS
7. Have sufficient visual acuity without the use of eyeglasses (contact lens use is acceptable) to accurately assess their facial wrinkles
8. Be willing to refrain from receiving facial fillers, laser treatments, use of any product that affects skin remodeling, or a product that may cause an active dermal response in the treatment areas (e.g., above the inferior orbital rim) from screening through the end of the study
9. All women of childbearing potential (WOCBP) must have a negative urine pregnancy test (UPT) result at the Screening Visit and must practice an effective method of contraception throughout the study (e.g., oral contraceptive pill, injection, implant, patch, vaginal ring, intrauterine coil, intrauterine device, tubal ligation, barrier method) used WITH an additional form of contraception (e.g., sponge, spermicide or condom); abstinence; no heterosexual intercourse; or has a vasectomized partner (refer to Section 5.6 for additional information)
10. Able to understand the requirements of the study and be willing and able to follow all study procedures, attend all scheduled visits, and successfully complete the study.

[figure not shown]

Massachusetts	20.5
Connecticut	20.0
Rhode Island	19.5
New York	19.0
Vermont	18.5
New Hampshire	18.0
Maine	17.5
District of Columbia	11.0
Maryland	16.5
Virginia	16.0
North Carolina	15.5
South Carolina	15.0
Georgia	14.5
Mississippi	24.0

[REDACTED]

[REDACTED]

[REDACTED]

[REDACTED]

### **5.3. Informed Consent and Authorization to Release Health Information**

Written informed consent will be obtained from all subjects before any study-related procedures (including any screening procedures) are performed. The investigator may discuss the trial and the possibility for entry with a potential subject without first obtaining consent. However, a subject wishing to participate must give written informed consent prior to any study-related procedures being conducted, including those performed solely for the purpose of determining eligibility for study participation, and including withdrawal from current medication (if required prior to study entry). The investigator has both the ethical and legal responsibility to ensure that each subject being considered for inclusion in this trial has been given a full explanation of the procedures and expectations for study participation, as well as ample time to decide whether or not to participate and have all questions answered satisfactorily.

The site-specific informed consent must be forwarded to Revance or designee for approval prior to submission to an Investigational Review Board (IRB)/Independent Ethics Committee (IEC) that is registered with the US Department of Health and Human Services or applicable health authority. Each subject will sign the consent form that has been approved by the same IRB/IEC that was responsible for protocol approval. Each informed consent document must adhere to the ethical principles stated in the Declaration of Helsinki and will include the elements required by FDA regulations in 21 CFR Part 50, as well as the elements required by ICH GCP guideline, and applicable federal and local regulatory requirements. The consent form must also include a statement that Revance, their designees, and auditing regulatory agencies will have direct access to the subject's records and medical history for study related purposes.

Once the appropriate essential information has been provided to the subject and fully explained by the investigator (or a qualified designee) and it is felt that the subject understands the implications and risks of participating in the trial, the IRB/IEC approved consent document shall be signed and dated by both the subject and the person obtaining consent (investigator or designee), and by any other parties required by the IRB/IEC or other regulatory authorities. The subject will be given a copy of the signed informed consent document with the original kept on file by the investigator. All of the above activities must be completed before any study related procedures are conducted (including any screening study procedures).

### **5.4. Lifestyle Considerations**

While enrolled in this study, subjects must agree to refrain from receiving non-ablative laser or light treatments, microdermabrasion, or chemical peels (medium depth or deeper, for example TCA or phenol) in the treatment areas within 3 months before enrollment through the end of the study. Subjects must not have brow tattoos or microblading within 3 months of enrollment or plan to have these procedures through the end of the study. Subject must also avoid upper facial hair removal in the treatment areas above the orbital rim (e.g., waxing, plucking, or threading)

for a total of 6 weeks during the study (2 weeks before GL treatment and 4 weeks after FHL treatment).

Refer to Section 6.4 for a complete list of prohibited medications during the study.

## **5.5. Protocol Deviations**

This study will be conducted as described in this protocol, except for emergency situations in which the protection, safety, and well-being of the subject requires immediate intervention, based on the judgment of the investigator (or a responsible, appropriately trained professional). In the event of a significant deviation from the protocol due to an emergency, accident, or mistake, the investigator or designee must contact Revance or designee by telephone at the earliest possible time. This will allow an early joint decision regarding the subject's continuation in the study. This decision will be documented by the investigator and Revance or designee.

## **5.6. Pregnancy**

All WOCBP must use an effective method of birth control throughout the study, (e.g., oral contraceptive pill, injection, implant, patch, vaginal ring, intrauterine coil, intrauterine device, tubal ligation, barrier method) used WITH an additional form of contraception (e.g., sponge, spermicide or condom); abstinence; no heterosexual intercourse; or has a vasectomized partner. A female is of childbearing potential UNLESS she is post-menopausal (no menses for 12 consecutive months) or without a uterus and/or both ovaries.

Before enrolling WOCBP in this study, investigators must review guidelines about study participation for WOCBP with the subject. The topics should generally include:

- Informed consent form content
- Pregnancy prevention information
- Risks to unborn child(ren)
- Any drug interactions with hormonal contraceptives
- Contraceptives in current use
- Guidelines for the follow-up of a reported pregnancy

Prior to study enrollment, WOCBP must be advised of the importance of avoiding pregnancy during participation in this study and the potential risk factors for an unintentional pregnancy. The subject must sign the informed consent document stating that the above-mentioned risk factors for unintentional pregnancy and the consequences were discussed with her.

During the study, all WOCBP should be instructed to contact the investigator immediately (within 24 hours) if pregnancy is suspected (e.g., missed or late menstrual cycle). The investigator, or qualified designee, must immediately notify Revance or designee of any female subject who becomes pregnant any time during study participation, record the information on the Pregnancy Notification Form and send the form to Revance or designee. Subjects will remain enrolled in the study but will not be treated. The investigator will be asked to follow-up with a phone call with the subject periodically throughout the pregnancy and post-delivery as applicable for ongoing health and safety information, as applicable.

[figure not shown]
If a serious adverse event (SAE) occurs in conjunction with the pregnancy such as untoward outcome of the pregnancy or of the offspring (spontaneous abortion, or abnormality in the offspring) then the reporting time frame for an SAE must be met and SAE reporting procedures followed. In the event of a normal birth follow-up with the subject will occur with a phone call until the first well baby visit to ensure no SAEs are identified in the neonate, at which time active follow-up to the pregnancy will cease.

## 6. Study Intervention

The active pharmaceutical ingredient, daxibotulinumtoxinA, is a purified 150 kilodalton (kDa) botulinum neurotoxin type A, derived from the Hall strain *C. botulinum*. Produced by *C. botulinum* as a single inactive polypeptide chain of 150 kDa, daxibotulinumtoxinA undergoes proteolytic cleavage by proteases present in the fermentation culture to yield the active di-chain molecule comprised of a 100 kDa heavy chain and a 50 kDa light chain linked via both non-covalent interactions and a disulfide bond (Aoki 2001). The heavy chain plays a role in cell binding, internalization, and translocation of daxibotulinumtoxinA into nerve cells. The light chain acts as a site-specific metalloprotease causing selective cleavage and inactivation of the 25 kDa synaptosome associated protein (SNAP-25) which is a cell membrane localized component of the vesicular release machinery. This cleavage of SNAP-25 by the light chain of botulinum toxin type A blocks the synaptic vesicle exocytosis and subsequent release of acetylcholine, thus leading to a dose-dependent weakening of the target muscle.

## 6.2.4. Investigational Product Administration

Investigational product will be administered by the PI to injection site in the designated treatment area. [REDACTED]

1. Wear protective gloves for investigational product administration
2. Pull subject's hair away from the treatment areas (forehead)
3. Wipe all injection sites with alcohol

[REDACTED]

[REDACTED]

[REDACTED]

[REDACTED]

[REDACTED]

[figure not shown]
[REDACTED]

[figure not shown]
### **6.3. Concomitant Medications/Therapies**

Concomitant medications are any prescription or over-the-counter preparations used by subjects during participation in the study. Use of concomitant medications will be recorded on the Concomitant Medications electronic case report form (eCRF) beginning at the Screening Visit (and including anything taken during the previous 30 days) until the Final Evaluation Visit.

The dose and dosing regimen of all prescription and non-prescription therapies and medications, including herbs, vitamins, or other nutritional supplements administered will be documented.

[REDACTED]

## **6.5. Dose Modification**

Subjects may receive up to 2 treatments in this study (1 GL treatment and 1 FHL treatment) depending on the evaluation of the DRC. The DRC may elect not to proceed with FHL treatment in a given dose cohort. Therefore, subjects may receive the GL treatment and not the FHL treatment in a dose cohort.

## 7. Discontinuation of Study Intervention and Subject Discontinuation/Withdrawal

### 7.1. Subject Discontinuation/Withdrawal from the Study

A subject may voluntarily withdraw from study participation at any time. If the subject withdraws consent and discontinues from the study, the investigator will attempt to determine the reason for discontinuation and record the reason in the subject's study records and on the eCRF. If a subject withdraws consent because of an AE, that AE should be indicated as the reason for withdrawal. In the event of early discontinuation, (i.e., prior to the Final Evaluation) where consent was not withdrawn, the subject should be asked to return to the study center to complete the assessments specified in the Final Evaluation Visit. Subjects who withdraw from the study will not be replaced. Subjects who withdraw from the study, but agree to continued follow-up, must be reconsented by the investigator for this limited participation in the study (unless this situation was adequately described in the original informed consent form [ICF]).

If at any time during the study, the investigator determines that it is not in the best interest of the subject to continue, the subject will be discontinued from participation. The investigator can discontinue a subject from study participation at any time if medically necessary or if the subject has failed to follow study procedures or keep follow-up appointments. Appropriate documentation in the subject's study record and eCRF regarding the reason for discontinuation must be completed. Prior to discontinuing a subject from study participation, the investigator will discuss his/her intentions with the Medical Monitor or designee.

All subjects who fail to return to the study center for the required follow-up visits will be contacted by phone to determine the reason(s) why the subject failed to return for the necessary visit or elected to discontinue from the study. If a subject is unreachable by telephone after a minimum of two documented attempts (one attempt on two different days), a registered letter will be sent requesting that contact be made with the investigator.

Revance has the right to terminate or to stop the study at any time. Should this be necessary, both Revance and the investigator will ensure that proper study discontinuation procedures are completed.

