### 8.2.5. Final Evaluation Visit (Week 38)

The following procedures must be performed and recorded at the Final Evaluation Visit for each subject. Following treatment, subjects will be followed for at least 24 weeks from GL treatment for safety or until all scores on the IGA-FWS and PFWS, as well as the IGA-FHWS and PFHWS return to baseline (Day 1 Visit) or until Week 38, whichever occurs first. Subjects will then have a Final Evaluation Visit at which time the following procedures must be performed and recorded:

8. Perform a physical examination

(hematology, serum chemistry, and urinalysis)

13. Conduct patient education for GL and FHL evaluation: Discuss the potential effect of DAXI for injection treatment, explain the PFWS measurement and the categories

of the severity assessment scales, and instruct the subjects to consider depth of lines for severity of their glabellar lines. Use the provided Patient Education Brochure

[REDACTED]

[REDACTED]

[REDACTED]

16. Assess for any new or ongoing AEs since the last visit

[REDACTED]

[REDACTED]

If there are no safety concerns, the subject's participation in the study is complete at this visit.

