## **2.2.2 Safety Endpoints**

The primary safety endpoint is the incidence, severity, and relationship to study drug of TEAEs and SAEs during the overall study duration.

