### 6.5.1 Primary Efficacy Analysis

The proportion of subjects achieving a score of 0 or 1 (none or mild) on the IGA-FHWS at maximum eyebrow elevation at Week 6 will be summarized. Subjects with no data at Week 6 after imputation of worst value will be considered to not meet the criteria (i.e., are imputed as non-responders). An exact 95% confidence intervals for the individual proportions will also be provided. A Cochran-Mantel-Haenszel test of association, stratified by stratified by baseline IGA-FHWS severity and study center, will be performed. In addition, an exact Cochran-Armitage test for trend, ignoring the stratification factors, will be performed. If the Cochran-Mantel-Haenszel test is significant at the 0.05 significance

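### Section 7.1 lets the investigator end participation for missed visits or non-adherence; after the Week 2 injection this stops only observation, so data collection should continue

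*Protocol*

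**What the plan says.** **The rule.** At any time, under Protocol Section 7.1, the investigator may remove someone from the study "if medically necessary or if the subject has failed to follow study procedures or keep follow-up appointments". It sets no cut-off relative to the injections and no minimum number of failures.

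**The treatment.** Protocol Section 4.4: "subjects will be treated with investigational product at the Day 1 Visit for GL and at the Week 2 visit for FHL". Section 6.5 allows at most these two treatments. Follow-up is far longer: under Section 8.2.5, "subjects will be followed for at least 24 weeks from GL treatment for safety", or until all severity scores return to baseline, or until Week 38, whichever is first. SAP Section 3.1 adds an intention of 24 weeks from the FHL injection (Week 26).

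**What follows removal.** Where consent was not withdrawn, Section 7.1 says "the subject should be asked to return to the study center to complete the assessments specified in the Final Evaluation Visit". Before a discontinuation, "the investigator will discuss his/her intentions with the Medical Monitor or designee". Continued follow-up is mentioned only for subjects who themselves withdraw, with re-consent unless the original consent form already covers it. Section 7.2 asks sites to contact and counsel subjects who miss visits, and to reschedule, before calling them lost to follow-up.

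**How the data are then handled.** SAP Section 6.5.1: "Subjects with no data at Week 6 after imputation of worst value will be considered to not meet the criteria". SAP Section 6.5 uses the population count as the denominator of every proportion at every visit, whatever was observed. SAP Section 4.3 admits to FHL-Evaluable only subjects with the FHL injection and at least one later IGA-FHWS rating at maximum eyebrow elevation. The primary safety endpoint in SAP Section 2.2.2 is "incidence, severity, and relationship to study drug of TEAEs and SAEs during the overall study duration".

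**The concern.** Once the Week 2 injection has been given, ending participation for poor attendance withholds no treatment. Its only effect is to stop the data. A missed call or late visit does not make a later wrinkle rating or adverse-event report invalid, so the trial gives up usable observations from subjects who still consent.

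Two features make this worth correcting. First, the analysis does not treat the lost data neutrally: depending on timing, the subject is either excluded or counted as a non-responder. Second, the study is open-label with sequential, non-randomized cohorts. The investigator who may remove a subject therefore knows the dose and, from Week 4, has usually rated the forehead. Nothing in the documents suggests that removals would depend on dose or result, but the wording leaves room for removal rates to differ between cohorts, and each cohort has only 15 subjects.

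**Working it through.** **1. The plan's own figure.** Protocol Section 4.1 gives four cohorts of 15: 4 × 15 = 60, matching the stated total. Section 9.1 says the size is not power-based, and no dropout allowance is visible. One subject is worth 1/15 = 6.7 points of a cohort's response rate.

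**2. Consequence by time of removal.** Week 3 is a phone call, so Week 4 is the first scheduled clinic visit after the FHL visit. I take the FHL efficacy population named in SAP Section 6.5 to be FHL-Evaluable. Follow-up forgone is 24 or 38 minus the week of removal.

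| Removed | Treatment still to come | Week 6 primary endpoint | Later by-visit rates | Weeks forgone, to Week 24 / Week 38 |
|---|---|---|---|---|
| Day 1 to Week 2, before the FHL injection | FHL injection | Not in FHL-Evaluable | Not in FHL-Evaluable | at least 22 / 36 |
| After FHL injection, no later rating | None | Excluded | Excluded | up to 22 / 36 |
| After a post-FHL rating, before Week 6 | None | Non-responder | Non-response | 20 / 34 if at Week 4 |
| Just after Week 6 | None | Unchanged | Non-response at each later visit | 18 / 32 |

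The second row changes if the exit visit includes an IGA-FHWS rating. The subject would then enter FHL-Evaluable and, unless the rating were assigned to Week 6, be scored as a non-responder.

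**3. Size for the primary endpoint.** Exact 95% limits: lower = 2.5% point of Beta(x, n − x + 1); upper = 97.5% point of Beta(x + 1, n − x). I assume 12 true responders of 15, and that k of them (k = 0 to 3, also assumed) are removed and would have attended Week 6.

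| k | Scored as non-responders | Excluded from FHL-Evaluable |
|---|---|---|
| 0 | 12/15 = 80.0% (51.9 to 95.7) | 12/15 = 80.0% (51.9 to 95.7) |
| 1 | 11/15 = 73.3% (44.9 to 92.2) | 11/14 = 78.6% (49.2 to 95.3) |
| 2 | 10/15 = 66.7% (38.4 to 88.2) | 10/13 = 76.9% (46.2 to 95.0) |
| 3 | 9/15 = 60.0% (32.3 to 83.7) | 9/12 = 75.0% (42.8 to 94.5) |

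The two routes differ: one removed responder costs 6.7 points by the first and 80.0 − 78.6 = 1.4 points by the second. The left-hand arithmetic also applies to each visit after Week 6 at which a removed subject would still have responded.

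**4. Size for safety.** The chance of seeing at least one case of an event with rate p among n subjects is 1 − (1 − p)^n. Comparing 15 fully followed subjects with 13, at assumed rates:

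- p = 2%: 26.1% against 23.1%
- p = 5%: 53.7% against 48.7%
- p = 10%: 79.4% against 74.6%

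This treats the two removed subjects as contributing nothing, so it is an upper bound on the loss. Events before exit and at the exit visit still count.

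**The case against.** A reader might infer that every removal turns a responder into a non-responder and that safety follow-up is lost. The documents do not support either.

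- **Analysis set.** A subject removed around Week 4 with no post-FHL rating is outside FHL-Evaluable and is not scored at all. Conversion to non-response needs a post-FHL rating and no Week 6 value, which is a narrow window.
- **Counterfactual.** A subject who would have skipped Week 6 anyway is a non-responder under the SAP with or without removal.
- **Safety.** Follow-up is shortened, not lost. An exit visit is requested and adverse events are assessed there (Section 8.2.5). Clinically significant study-related events are followed beyond the end of study (Section 8.5.5), and serious events are followed up and related late ones reported (Section 8.5.6). Because follow-up may end when scores return to baseline, and no visit falls at Week 24, the 24-week figure is not a firm comparator.
- **Safeguards.** The power is permissive, the Medical Monitor is consulted first, and missed visits are chased and rescheduled.
- **Treatment left to stop.** Between Day 1 and Week 2 the FHL injection is still to come. The protocol also provides elsewhere for subjects who stay in the study without further treatment: after a pregnancy (Section 5.6), or when the Data Review Committee withholds the FHL dose (Section 4.1.1).

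All of this stands and limits the size of the problem. It does not close the gap. The exit visit is a single visit, the Medical Monitor's agreement is not required, and continued follow-up is stated only for subjects who withdraw. Section 7.2 tells sites to reschedule after missed visits, while Section 7.1 permits removal for the same conduct.

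**Conclusion.** The point holds as a cheap improvement. After Week 2, the conduct ground in Section 7.1 ends observation only, and a consenting subject removed under it has no stated route to the remaining visits beyond one requested exit visit.

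The primary endpoint is affected in two cases: 6.7 points per true responder removed after a post-FHL rating and before a Week 6 visit that would have been attended, and exclusion from FHL-Evaluable for a subject with no post-FHL rating. Removals after Week 6 do not touch it but depress the later by-visit responder rates, because the denominators are fixed. Adverse-event collection for the overall-duration endpoint is shortened.

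A claim that the cohort comparison is biased would go further than the documents allow: they show the opportunity, not that removals differ by dose. The number of removals is unknown, and the 0 to 3 per cohort used here is an assumption. The visit-windowing rules, the worst-value imputation rule and the full schedule of assessments are not readable, so an exit visit or imputed value near Week 6 might fill some gaps. Protocol Section 9.3 says no imputation of missing data is planned, whereas SAP Section 6.5.1 imputes non-response. The two should be reconciled; the non-response results above follow the SAP.

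**What to change.** In Protocol Section 7.1, separate ending participation from ending data collection, for the conduct ground only:

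- Once any injection has been given, record missed visits and failure to follow procedures as protocol deviations. By themselves they are not grounds for ending data collection.
- Scheduled IGA-FHWS and adverse-event assessments continue unless the subject withdraws consent.
- If the subject will not attend in person, collect adverse events by phone, as is already done at Weeks 1 and 3.

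Leave unchanged the medical-necessity and best-interest grounds, the Medical Monitor discussion, and the re-consent sentence for subjects who withdraw.

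The cost is a few sentences of protocol text, since the visits are already scheduled. The downside is some chasing of poorly compliant subjects and a few late or out-of-window visits.
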